**Hypothesis 1.** Based on numerous studies, including our own pilot data, that suggest CBD may be anxiolytic and mitigate the harmful effects of THC, we hypothesize a step wise effect of strain such that the -THC/+CBD group will demonstrate the lowest anxiety, as compared to the +THC/+CBD group(s), which will have lower anxiety levels than the +THC/-CBD and non-using control groups. *In addition to strain assignment, CBD and THC blood levels will also be tested in relation to anxiety, with greater CBD levels associated with lower levels of anxiety.*

**Aim 2:** Based on the notion that CBD decreases inflammation and acute stress, the study will examine: **1) circulating inflammatory markers and 2) behavioral and biological markers of stress reactivity** in mild to moderately anxious marijuana users exposed to one of three marijuana strains: 1) +THC/-CBD, 2) +THC/+CBD, or 3) -THC/+CBD versus a matched (non-using) group.

**Hypothesis 2A.** There will be a main effect of strain such that the -THC/+CBD group will have the lowest levels of circulating peripheral inflammatory markers, as compared to the +THC/+CBD group(s), which will have lower levels than the +THC/-CBD and non-using control groups. *In addition to strain assignment, CBD and THC blood levels will also be tested in relation to inflammation, with CBD levels associated with lower levels of inflammation.*

**Hypothesis 2B.** There will be a main effect of strain such that the -THC/+CBD strain group will have the lowest levels of stress-reactivity to a laboratory stressor (measured via self-report, physiological, and inflammatory stress responses), as compared to the +THC/+CBD group(s), which will have lower levels of reactivity than the +THC/-CBD and non-using control groups. *In addition to strain assignment, CBD and THC blood levels will also be tested in relation to stress-reactivity outcomes, with CBD levels associated with less stress-reactivity.*

**Aim 3:** Based on the notion that the effects of CBD on inflammation or stress may mediate the effects of marijuana on anxiety, the study will **examine the mechanisms by which CBD influences anxiety.**

Hypothesis 3. We will estimate a mediational model that tests whether the effect of marijuana strain on anxiety is mediated by changes in circulating inflammatory markers, stress-reactivity, or both.

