THC is well known for having immediate negative effects both acutely and potentially even over the longer term on anxiety, suggesting that higher potency THC strains could have negative consequences that exacerbate anxiety. CBD, on the other hand, is non-psychoactive, has high tolerability in humans, and may counteract some of the negative cognitive effects of THC, at least in the short term (see Preliminary Studies). Further, protective effects of CBD have been widely shown in preclinical models of inflammation and anxiety. In order to determine: 1) whether marijuana has effects on anxiolytic and inflammatory processes, 2) whether these effects

are more likely to be due to THC, CBD, or some combination of the two, and 3) to provide data on the minimization of harm due to marijuana use with respect to anxiety symptoms, the current study will quantitatively assess THC and CBD blood levels in mildly to moderately anxious marijuana users who have a desire to use cannabis to cope with their anxiety and will use one of three different strains of marijuana (that vary in their levels of THC and CBD). These participants (marijuana users) will be compared to a matched control group that does not currently use or have a desire to use marijuana to cope with their anxiety. We propose that the opposing pharmacology effects of THC and CBD may result in differing inflammation and stress-reactivity profiles in anxious marijuana users as compared to anxious non-users.

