*The impact of attrition.* It is anticipated that some attrition will occur. Based on our current pilot study and previous marijuana studies, we anticipate a 10-15% attrition rate between the baseline session and the final four-week follow up session, though we have not experienced and do not anticipate differential attrition by condition. Thus, to allow for attrition, we assume an approximate 85% retention rate over the course of data collection. To adjust for this attrition rate in all groups, we will recruit  $n\approx520$  participants ( $n=86$ /flower or control group as well as 58/edible group). Our approach to power analysis and accounting for attrition is also quite conservative, in that the techniques we will utilize in data analysis use state of the art recommendations for the handling of missing data in longitudinal studies.

**Statistical Analysis Plan.** Analyses will be conducted primarily on the SAS system for Windows Version 9.4 and Mplus Version 7.3, which include capabilities to test multilevel models that appropriately model both normally and non-normally distributed data as well as missing data. To test the success of random assignment across the marijuana strain groups the equivalence of the three marijuana user and control groups across all pretest measures will be assessed via  $t$ -tests on continuous items (e.g., BAI) and  $\chi^2$  tests of categorical items (e.g., race). The Bonferroni approach will be used to correct for alpha inflation (familywise alpha of .05). The distributional properties of continuous variables will be examined to determine appropriate analytic techniques or normalizing transformations prior any analyses.

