**Specific Aim 1** – To compare changes in anxiety in mild to moderately anxious marijuana users exposed to 4 weeks of use of one of three different marijuana strains (+THC/-CBD vs. +THC/+CBD vs. -THC/+CBD) to a group of non-using controls matched on anxiety. *Hypothesis 1* predicts a main effect of strain such that -THC/+CBD marijuana users will have lower levels of anxiety (BAI) compared to other marijuana groups and to non-using controls. To examine the main effects of group on these outcomes, we will estimate a random coefficient regression (RCR) models in SAS Proc Mixed wherein the change in BAI scores will be regressed on marijuana user group, time, and the groupXtime interaction. *Hypothesis 1* also predicts that higher CBD levels in blood among marijuana users will be associated with lower BAI. The analysis for this hypothesis will again be a RCR model, but instead of group membership, the independent variables in these models will be level of CBD in blood, time, and the CBDxtime interaction. We will conduct additional models to explore whether there may also be main effects of THC in blood or a THCXCBD interaction effect on BAI. Secondary models will test the effects of strain and /or cannabinoid blood levels on the daily and monthly assessments of anxiety using a multi-level modeling approach. These additional analyses will appropriately control for Type I error, depending upon the number of tests run. Co-I [name] has used such models extensively in prior work.

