**Specific Aim 3** - To test indirect effects of marijuana use on anxiety (BAI) via inflammatory markers and stress reactivity in anxious marijuana users exposed to 4 weeks of use of one of three different marijuana strains compared to a group of non-using controls matched on anxiety. Hypothesis 3 will test mediational models that ask whether the effect of marijuana use and strain on anxiety is mediated by changes in inflammation, stress reactivity, or both. To this end, we will estimate the mediational models in Figures 3a and 3b via structural equation modeling. To test the overall effect of use of marijuana versus non use, we will estimate model 3a wherein the sole exogenous variable is marijuana users (coded as 1) versus non-users (coded as 0). The mediators will be change in inflammation from Session 1 to Session 3 and stress reactivity at Session 3. The outcome variable is change in anxiety from Session 1 to Session 3. This model will be estimated and both the fit of the model and the significance of the path coefficients will be examined. Importantly, we will compare the path coefficients from user status to inflammation versus stress reactivity to determine whether use is associated with changes in inflammation, stress reactivity, or both. Assuming that the paths from inflammation and stress reactivity to anxiety are significant, we can test whether there are indirect effects of user status on anxiety that are mediated by inflammation, stress reactivity, or both. A test for completeness of mediation is employed through a 1 degree of freedom  $\chi^2$  test where a path directly from user status to anxiety is added to the model. A nonsignificant direct path and a nonsignificant change in  $\chi^2$  suggest that user group effects on the anxiety were mediated through the theoretical mediational constructs. A secondary test of mediation will utilize bootstrap methods to test the significance of, and confidence limits around, the mediated effect. Similar mediational analyses have been widely used by Co-I [name]. The model depicted in Figure 3b will test the more focused hypothesis that the ratio of cannabinoids is critical for the biological and behavioral changes that drive anxiety. The analysis will follow identical procedures to those described to test Model 3a. Finally, it is also possible to use continuous values of THC and CBD in blood as the exogenous predictors in the model.

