We expect to see changes in abundance and diversity of microbiota populations found in the gut as a result of cannabis use. Because substance use, inflammation, and the gut microbiome, as well as pain and anxiety, and inflammation and the gut microbiome are all heavily intertwined (Fung et al 2017, Gorky & Schwaber 2016, Leclercq et al 2014, Mayer et al 2015, Peterson et al 2017), we will examine the relationship between changes in the gut microbiome with changes in anxiety and inflammatory biomarkers in the blood (cytokines and blood monocyte cell response to LPS challenge) as a result of cannabis use. Microbial DNA will be extracted from fecal samples and then analyzed to determine how many and which bacterial species are present in the gut. Gut microbiome data will be collected at two time-points during this study, once before and one after study cannabis use (i.e., with assigned cannabis ratios).

**Daily (Online-based message) follow-up Assessments.** Ecological momentary assessment of marijuana use via messaging has been shown to be feasible in a variety of marijuana users. During the 4 week study, marijuana users will answer online survey assessments via email with individually tailored links hosted by our university's licensed survey tool RedCap. During the 4-Week study period, participants will report *daily* on the anxiety, their marijuana use, other stress management strategies, and their sleep pattern. This brief message report will provide a daily repeated measure of our primary constructs (anxiety and marijuana use) and potential mediators or moderators over the course of the 4-Week study. All subjects will be given extensive instructions on completing the daily message at the Baseline Appointment and will practice answering the questions in the lab using their cell phone or a lab computer to ensure they understand the process and time commitment. To enhance the response rate, participation on daily message follow-ups will be monitored and participants will be contacted if they do not respond for two consecutive days of daily messages. Participants will then be compensated for their time and effort during the 2-Week and 4-Week Appointments, receiving a \$1/day with a \$5 bonus for completing 13 of 15 online follow up message reports for each two-week period (\$40 in total possible).

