### **XVI. RISKS TO PARTICIPANTS**

**Risks Pertaining to the Legality of Cannabis.** The possession and use of cannabis is legal at the state level but illegal at the federal level. Any risk associated with this study is not greater than risks experienced by participants normally, since a participant in the cannabis groups must be regular cannabis users to be in the study. We will comply with all NIH guidelines, and a

Certificate of Confidentiality will be deemed applicable for our study, decreasing the risk for participants.

**Risks Associated with Venipuncture.** There is a small risk of local hematoma, infection, and syncope associated with phlebotomy. Any risk associated with undergoing four blood draws for a total of 160 ml over ~ five hours in three separate days will be minimized with certified and experienced venipuncture staff, collecting information on the subjects last meal and by offering a standard snack before the last blood draw.

**Psychological Risks and Discomforts.** While participants who use cannabis in the context of the research must already be experienced cannabis users in order to be in the study, it is still possible that some participants might experience some adverse effects from the cannabis such as changes in mood/affect, sleepiness, paranoia, and increased heart rate. There is a slight risk that using cannabis may be associated with a psychotic episode. However, participants will be monitored during the study period by the PI [name] who is a licensed clinical psychologist (Colorado license #4116) to make sure that there are no clinically significant events that occur. Increases in anxiety or discomfort will be monitored and should clinically severe or impairing anxiety be present, the participants will be removed from the study and referred to appropriate mental health treatment. This practice has been used frequently by the PI in other IRB approved studies and the risks for clinically meaningful increases in anxiety are not expected to be greater than what would be experienced in daily living. Information regarding anxiety treatment resources and appropriate referrals will be made to each participant at the end of participation, if requested.

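### Participants removed for severe anxiety give no BAI at or after removal, so removals between visits could pull the Aim 1 strain difference toward zero

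*Combined protocol and SAP*

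**What the plan says.** Section XVI (Risks to Participants, psychological risks) has staff monitor rises in anxiety and adds that "should clinically severe or impairing anxiety be present, the participants will be removed from the study and referred to appropriate mental health treatment". It names no instrument, cut-off or expected rate. It does say that clinically meaningful rises should be no more likely than in ordinary life.

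In the Statistical Analysis Plan of section IV, Specific Aim 1 states that "the change in BAI scores will be regressed on marijuana user group, time, and the groupXtime interaction". For Specific Aim 3, "The outcome variable is change in anxiety from Session 1 to Session 3". Table 2 schedules the BAI at baseline, week 2 and week 4 before self-administration, each time covering the past week. For people who leave early, section XV describes only pro-rated payment.

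On direction, Hypothesis 1 in section I reads "we hypothesize a step wise effect of strain such that the -THC/+CBD group will demonstrate the lowest anxiety", with +THC/-CBD and the non-using controls at the high end. The Background discusses lasting effects of THC on anxiety, "suggesting that higher potency THC strains could have negative consequences that exacerbate anxiety". On dropout, the attrition paragraph of section IV says "we have not experienced and do not anticipate differential attrition by condition". Daily anxiety reports exist, but their role is limited: "Secondary models will test the effects of strain and /or cannabinoid blood levels on the daily and monthly assessments of anxiety".

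**The concern.** The rule that ends a participant's measurement is triggered by the construct being measured. A likelihood-based mixed model handles such losses correctly when the recorded BAIs explain who was lost. It does not when anxiety rises between two scheduled BAIs and the participant is removed before the next one. The last recorded BAI then describes a week before the episode, and the model predicts a week-4 value that is too low.

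If the sponsor's hypothesis is right, this happens more often in the more anxious arms. Their estimated means fall further than that of -THC/+CBD, and the arms move together. A real strain effect could be understated or missed, and the Session 1 to Session 3 anxiety change in Aim 3 would lose the same people.

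**Working it through.** **Inputs from the documents (section IV).** Required per strain, flower plus edible: 75 + 50 = 125. Recruited per strain: 86 + 58 = 144. The plan's total reproduces: 4 × 86 + 3 × 58 = 518, stated as about 520. Implied attrition is 1 − 125/144 = 13.2%, inside the stated 10-15%. The correlation between assessments is .50.

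**Assumptions not in the documents.** BAI has SD 1. The true week-4 difference between -THC/+CBD and +THC/-CBD is d = 0.35, with half of it (0.175) present at week 2. Of the -THC/+CBD arm, 1%, 2% or 5% is removed, half in weeks 0-2 and half in weeks 2-4, and the same severity threshold applies in both arms.

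**Step 1: removals by arm.** At the 2% rate, each interval removes 1% of -THC/+CBD, so the threshold is z = 2.326. In +THC/-CBD the distances are 2.326 − 0.175 = 2.151 and 2.326 − 0.35 = 1.976. The tail areas are 1.57% and 2.41%, about 4% in total. The same steps turn 1% into about 2% and 5% into about 9% (8-9% in simulation). Out of 144 people this is roughly 1 against 3, 3 against 5 or 6, and 7 against 12 or 13.

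**Step 2: bias by hand, least favourable mechanism.** Suppose severity at removal equals the next BAI, which is never recorded. With φ the normal density, an arm's estimated week-4 mean is too low by approximately

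(ρ − ρ²)·φ(z₂) + (1 − 2ρ²/(1 + ρ))·φ(z₄)

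The first term is for removal before week 2, when only the baseline BAI is known. The second is for removal between weeks 2 and 4. At ρ = .5 the weights are .25 and .667.

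| Rate in -THC/+CBD | Shift, -THC/+CBD | Shift, +THC/-CBD | Gap lost | Share of 0.35 |
|---|---|---|---|---|
| 1% | .917 × .0145 = .013 | .25 × .0223 + .667 × .0335 = .028 | .015 | 4.2% |
| 2% | .917 × .0267 = .024 | .25 × .0395 + .667 × .0566 = .048 | .023 | 6.6% |
| 5% | .917 × .0584 = .054 | .25 × .0811 + .667 × .1092 = .093 | .039 | 11.3% |

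**Step 3: simulation.** A maximum-likelihood repeated-measures model using all available BAIs stands in for the planned random coefficient regression. Random dropout brings total attrition to about 13%. With no removals the estimate is 0.350 and power is .81.

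| Rate | Severity = next BAI | Correlated .7 with it | Separate occasion, correlated .5 with every BAI | Power |
|---|---|---|---|---|
| 1% | 0.337 | 0.338 | 0.345 | .77-.79 |
| 2% | 0.327 | 0.333 | 0.344 | .74-.81 |
| 5% | 0.308 | 0.318 | 0.336 | .70-.80 |

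For example, 1 − 0.327/0.350 = 6.6%, which agrees with the hand calculation. Repeat runs reach 8.2% at the 2% rate and 13.1% at 5%. The power ranges overlap partly through simulation noise.

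**Step 4: when the bias vanishes.** If removal follows a high week-2 BAI that was recorded, the estimate is 0.349-0.351. A separate large-sample simulation, with true differences of 0.3 and 0.5 SD, recovers 98-101% of the truth in that case. Removal after the Session 3 BAI costs Aim 1 nothing.

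**Step 5: correlation.** At ρ = .7 the weights in step 2 fall to .21 and .424, and the 2% case becomes (.21 × .0395 + .424 × .0566) − .634 × .0267 = .015, or 4.4% of 0.35. Across all three rates and mechanisms, shrinkage at .7 is roughly 1-9%.

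**The case against.** The best counter-argument is that the documents describe little that would lead to removal between visits. The response procedures in section XVII centre on sessions: investigators are on call, two staff are in the mobile laboratory, and an investigator drives there if needed. The one session with cannabis use built in is Session 4, after the endpoint BAI. Between visits the routine contact is the daily report, and section XII describes checking it for non-response, not for severity. This stands as a limit on frequency. It does not remove the point, because section XVI has participants monitored throughout the study period, and the rule applies whenever severe anxiety appears. Eligibility also sets a floor on the GAD-7 but no ceiling.

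Second, a correlation of .50 is conservative for sample size but unfavourable here, since recorded BAIs then predict missing ones less well. That is right, and the size is stated accordingly.

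Third, the daily ratings already capture anxiety up to removal. They do, but only in secondary models. Used as auxiliary information (correlation .7 with severity), they would cut an 11.9% shrinkage only to 7.6%.

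A reader might infer that the strain difference must shrink whenever Hypothesis 1 is true. The documents do not support that, because the bias also needs removals on anxiety that no BAI has recorded. A reader might also infer that sections XV, XVI and XVII contradict each other on severe reactions. They overlap without saying which governs, but they do not conflict on their face.

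**Conclusion.** The point holds in conditional form. The removal rule acts on the Aim 1 construct and the plan secures no BAI at or after removal. If Hypothesis 1 is true and some removals precede the BAI that would have shown the rise, losses differ by strain, contrary to the attrition paragraph's expectation, and the mixed-model difference is biased toward zero.

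At a true 0.35 SD, correlation .5 and removals split evenly over the two intervals, the shrinkage is about 1-8% for 1-2% removed from -THC/+CBD and about 3-13% for 5%. Removal rate, true difference, timing and mechanism are all assumptions. Since section XVI expects such events to be rare, the lower rates are the more natural reading. Larger losses can be produced by putting every removal in weeks 2-4 and setting severity equal to the missing BAI, but nothing in the documents supports that combination. At a true 0.50 SD with the even split, power stays at .95 or above.

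A reader might also fear a false positive. This mechanism does not create a strain difference where none exists; it can only hide one. Priority is minor to moderate.

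**What to change.** In section XVI, replace removal from the study with stopping study procedures, advice to stop the product (for users) and referral for treatment. Record a BAI when that decision is made. Invite the participant to complete the remaining week-2 and week-4 BAI through RedCap, with the licensed principal investigator or a co-investigator reviewing each one.

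In the analysis, keep these participants in their assigned strain group and report their number by strain. Add one sensitivity analysis that gives them a week-4 BAI worse than the model predicts, for example by 0.5 and 1 SD.

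At the 5% rate, with severity equal to the next BAI, simulated shrinkage falls from 11.9% to 4.9%, 2.4% or 0.4% if 50%, 80% or 100% supply the remote BAI.

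The cost is a 21-item questionnaire and clinician review for a few participants. A BAI taken after stopping and referral reflects the assigned strategy, not continued use, which may dilute the contrast. Blood measures and stress reactivity stay missing, so Aim 3 regains its outcome but not its mediators for these people. The Spring 2023 amendment in section IV describes contact with participants who have finished, so new collection may come too late for some. The count by strain and the sensitivity analysis need no further contact.
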